## **7. RESEARCH METHODS**

### **7.1. Study Design**

This is a cohort study using data from the Veterans Affairs National Sample, which is composed of Veterans who receive healthcare services through the Veterans Health Administration (VHA). This national sample is representative of the Veteran population, capturing a wide range of demographic, clinical, and social characteristics.

Data will be extracted from VHA's Corporate Data Warehouse (CDW), a comprehensive, regularly updated repository of information from VHA's electronic health records and administrative files. It includes patient-level data such as demographics, clinical encounters (diagnoses, interventions), laboratory and imaging results, medication details, health services utilization, and long-term health outcomes.

The study period will range from January 1, 2021, to December 31, 2025. Initiation of PrEP regimen will be assessed during the period January 1, 2021 to June 30, 2025, to allow for at least 6 months of observation following PrEP initiation.

The study will include different cohorts, as described in Table 2.

Veterans who are not on PrEP but could benefit from PrEP will be identified based on risk factors for HIV acquisition or factors linked to behaviors increasing the risk of HIV acquisition which are generally documented in Veterans health records. These risk factors include: tested for or diagnosed with a bacterial STI in the past 12 months (gonorrhea, syphilis, chlamydia) (US CDC, 2024), tested for HIV in the past 12 months, ever had alcohol use disorder (Williams, 2016), ever used illicit non-injection drugs (HIV.gov, 2024), ever used injectable drugs (CDC, 2024), Black women (CDC, 2024; Reaves, 2025), men who have sex with men (CDC, 2022; Mayer, 2021), individuals aged 18-24 years (HIV.gov, 2025 b), any history of PrEP use (Hojilla, 2021; Krakower, 2019).

---

 The US CDC recommends PrEP for people with a bacterial STI diagnosis in the past 6 months. This has been extended to testing for a bacterial STI in the past 12 months for this protocol.

**Table 2:** Description of study cohorts

Objectives	Criteria	
Objective 1a - Among all Veterans without evidence of HIV infection	Population/exposure	No evidence of HIV diagnosis at beginning of each calendar year of the study period under analysis
	Index date	N/A
	Censoring criteria	N/A
	Endpoint	HIV diagnosis
Objective 1b - Among Veterans with a new HIV diagnosis during the study period	Index date	Date of HIV diagnosis
	Censoring criteria	NA
	Endpoint	PrEP use (never, use within 12 months before diagnosis, use >12 months before diagnosis)
Objective set 2 – among Veterans without evidence of HIV infection who are not on PrEP but could benefits from PrEP	Population/exposure	At least one of the following criteria: tested for or diagnosed with a bacterial STI in the past 12 months (gonorrhea, syphilis, chlamydia), tested for HIV in the past 12 months, ever had alcohol use disorder, ever used illicit non-injection drugs, ever used injectable drugs, Black women, men who have sex with men, individuals aged 18-24 years, any history of PrEP use
	Index date	First visit during the study period with criteria indicating the individual could benefit from PrEP
	Censoring criteria	Death, loss to follow-up, end of the study period, 12 months after index date, PrEP initiation, whatever comes first
	Endpoints	HIV testing, HIV diagnosis, Screening/testing for other STIs, STI diagnoses
Objective set 3 – among Veterans with a PrEP prescription	Exposure groups	Oral PrEP, CAB LA PrEP
	Index date	Start of first PrEP regimen during the study period (dispensing date for oral PrEP, injection date for CAB LA)
	Censoring criteria for calculation of proportion of days covered	Death, loss to follow-up (12 months after last clinical contact), study end, 12 months after index date whatever comes first
	Endpoints	Adherence to PrEP schedule, discontinuation and resumption of PrEP, STI screening/testing, STI diagnosis, STI treatment prescription, HIV testing and diagnosis

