## 7.2. Study Population and Setting

### 7.2.1. Inclusion criteria

- **Veterans in care without evidence of HIV infection (Obj. 1.1)- individuals will be included if they meet all of the following criteria:**

- At least one VHA health encounter in the calendar year
- $\geq 18$  years of age
- No evidence of HIV infection at the beginning of the calendar year under analysis

- **Veterans in care with a new HIV diagnosis (Obj. 1.2):**

- Incident HIV diagnosis (refer to definition in section 7.3.3)

- **Veterans in care without evidence of HIV infection who are not on PrEP but who could benefit from PrEP (Objective set 2)- individuals meeting all of the following criteria:**

- At least one VHA health encounter during the study period
- $\geq 18$  years of age
- Any of the following criteria indicating that the individual has a risk factor for HIV acquisition or a factor linked to behaviors increasing the risk of HIV acquisition and may benefit from PrEP:
  - tested for or diagnosed with a bacterial STI in the past 12 months (gonorrhea, syphilis, chlamydia),
  - tested for HIV in the past 12 months,
  - ever had alcohol use disorder,
  - ever used illicit non-injection drugs,
  - ever used injectable drugs,
  - Black women,
  - men who have sex with men,
  - individuals aged 18-24 years,
  - any history of PrEP use
- No evidence of HIV infection at the first health encounter with a criteria for PrEP

- **Veterans in care using oral PrEP only (objective set 3)**

- At least one VHA health encounter during the study period
- $\geq 18$  years of age
- Received at least one oral PrEP prescription (TDF/FTC, TAF/FTC) between January 1 2021 and 31 December 2024
- No evidence of HIV infection at the time of the first oral PrEP prescription in the study period
- Have not received a CAB LA PrEP injection between January 1, 2021, and June 30, 2025

- **Veterans in care using CAB LA for PrEP (objective set 3)**

- At least one VHA health encounter during the study period
- $\geq 18$  years of age
- Received at least one CAB LA PrEP injection between January 1, 2021 and June 30, 2025

- No evidence of HIV infection at the time of the first CAB LA PrEP injection in the study period

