#### ◆ People without HIV who are not on PrEP and could benefit from PrEP (Objective set 2)

##### ◆ HIV testing & STI screening (Objective 2.2)

- HIV testing
  - Frequency and rate of HIV tests over 12-month period following the index date

- Type of HIV tests
- HIV diagnoses
  - Frequency and rate of new HIV diagnosis within 12 months of index date (first visit with at least one criteria for PrEP)  
Follow-up (FU) will be censored at first of:
    - HIV diagnosis
    - 12 months after index date
    - End of the study period
    - Loss to follow-up
    - Death
- STI testing/screening
  - Frequency and rate of STI testing events, overall (testing for multiple STIs on the same day will count as 1 testing event) and by type of STI tested  
Type of STI:
    - Syphilis
    - Gonorrhea
    - Chlamydia
    - Chancroid
    - Lymphogranuloma venereum
    - *Mycoplasma genitalium*
    - Hepatitis B virus (HBV)
    - Hepatitis C virus (HCV)
    - Genital Herpes (HSV-1, HSV-2)
    - Trichomoniasis
    - Genital Human papilloma virus (HPV) including warts  
Follow-up (FU) will be censored at first of:
    - HIV diagnosis
    - 12 months after index date
    - End of the study period
    - Loss to follow-up
    - Death
- STI diagnoses
  - Frequency and rate of new diagnosis of STI as noted in medical record or positive test result
  - STI diagnoses for
    - Syphilis
    - Gonorrhea
    - Chlamydia
    - Chancroid
    - Lymphogranuloma venereum
    - *Mycoplasma genitalium*
    - Hepatitis B virus (HBV)
    - Hepatitis C virus (HCV)
    - Genital Herpes (HSV-1, HSV-2)
    - Trichomoniasis

- Genital Human papilloma virus (HPV) including warts

◆ **PrEP users (Objective set 3)**

◆ **Use of oral lead-in (Objective 3.2)**

CAB PrEP formulation at initiation: proportion with CAB oral lead-in (OLI) vs. direct to injection (DTI)

◆ **Adherence (Objective 3.3)**

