##### **Veterans who are not on PrEP and who could benefit from PrEP (Objective set 2)**

Baseline demographic and clinical characteristics will be described at the first visit during the study period meeting one of the criteria (index date), using median and interquartile ranges for continuous variables and counts and proportions for categorical variables. The frequency and rate (per 100 person-years) of HIV testing, HIV diagnoses, STI testing/screening, and STI diagnoses will be described within 12-months of the index date.

Rates of HIV tests and diagnoses as well as STI tests and diagnoses over this 12-month period will be estimated using univariate Poisson regression

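### Objective set 2 has two censoring lists that disagree on PrEP initiation and HIV diagnosis, and its itemised criteria do not put the off-PrEP restriction into effect

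*Protocol*

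**What the plan says.** **Cohort.** Section 7.2.1 heads the population as Veterans "who are not on PrEP but who could benefit from PrEP (Objective set 2)- individuals meeting all of the following criteria". The items that follow are an encounter, an age limit, at least one risk factor, and "No evidence of HIV infection at the first health encounter with a criteria for PrEP". The risk factors include "any history of PrEP use" and "tested for HIV in the past 12 months". Table 2 sets the index date as "First visit during the study period with criteria indicating the individual could benefit from PrEP". Neither place itemises PrEP status at index.

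**Censoring.** Table 2 ends follow-up for Objective set 2 at "Death, loss to follow-up, end of the study period, 12 months after index date, PrEP initiation, whatever comes first". Section 7.3.3, under Objective 2.2, prints its own list, introduced by "Follow-up (FU) will be censored at first of", once under HIV diagnoses and again under STI testing. That list has HIV diagnosis, 12 months after index, end of the study period, loss to follow-up and death. No list is printed there under HIV testing or STI diagnoses.

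**Analysis.** Section 7.7.1.1 states: "The frequency and rate (per 100 person-years) of HIV testing, HIV diagnoses, STI testing/screening, and STI diagnoses will be described". It does not say which list governs the person-years.

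**The concern.** Objective set 2 exists to describe HIV and STI testing and diagnoses among people off PrEP. The rates therefore depend on when a person leaves the risk set and on who enters it. The protocol gives two answers to the first question for two of the four endpoints. For the second it relies on a heading that no criterion carries out. Two programmers following different sections would build different denominators. The independent re-analysis in Section 7.8 works on the same data set and would not reliably expose a cohort rule that was never specified.

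The direction matters because Section 5 expects people on daily oral PrEP to be HIV-tested every 3 months. Person-time on PrEP carries many tests, and any of it counted here raises the off-PrEP testing rates.

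**Working it through.** **1. The two lists side by side**

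| Event ending follow-up | Table 2 | 7.3.3: HIV diagnoses, STI testing | 7.3.3: HIV testing, STI diagnoses |
|---|---|---|---|
| HIV diagnosis | no | yes | no list |
| PrEP initiation | yes | no | no list |
| 12 months, study end, loss to follow-up, death | yes | yes | no list |

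The contradiction therefore concerns HIV diagnoses and STI testing. For HIV testing and STI diagnoses, Table 2 is the only rule.

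Two hypothetical Veterans show what changes:
- PrEP started 3 months after index: Table 2 counts 0.25 person-years. Section 7.3.3 counts 1.00, of which 0.75 follow PrEP start.
- HIV diagnosed 3 months after index: Section 7.3.3 counts 0.25 person-years. Table 2 counts up to 1.00.

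**2. Can a current user enter, and would censoring remove that person?**

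A current user has a PrEP history and, if tested as Section 5 describes, an HIV test in the past 12 months. The itemised list is met at the first visit. Section 7.9 defines oral initiation as the first dispensing and treats later dispensings as renewals, so the next fill is not clearly an initiation. Objective 3.4 treats resumption as a separate event, so a former user who restarts is not clearly censored under Table 2 either.

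**3. Size**

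The protocol gives no figure to reproduce, so this is an illustration. Let f be the on-PrEP share of person-time, r0 the off-PrEP rate and r1 the on-PrEP rate.

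Observed rate = (1 − f)·r0 + f·r1, so the relative change is f·(r1/r0 − 1).

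From the protocol: 6,050 Veterans prescribed PrEP in 2022 (Section 5); 15,477 + 748 = 16,225 users over the initiation window (Section 7.5); r1 = 400 HIV tests per 100 person-years from 3-monthly testing (Section 5).
Assumed: cohort of 0.5 to 3 million; r0 of 20 to 100 HIV tests per 100 person-years; every counted user on PrEP for the whole 12 months.

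HIV testing with 6,050 users:
- 1 million, r0 = 50: f = 0.605%; 0.99395 × 50 + 0.00605 × 400 = 52.1, or +4.2%.
- Low end, 3 million, r0 = 100: f = 0.20%; 0.0020 × 3 = +0.6%.
- High end, 0.5 million, r0 = 20: f = 1.21%; 0.0121 × 19 = +23%.

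Extreme case, all 16,225 on PrEP throughout: +11.4% at 1 million and r0 = 50 (1.62% × 7); +1.6% to +62% over the whole range.

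STI diagnoses, gonorrhoea plus chlamydia only, assumed 0.5 off PrEP and 20 on PrEP per 100 person-years, so r1/r0 = 40:
- 3,000 users (assumed) in 3 million: 0.001 × 39 = +3.9%.
- 6,050 in 1 million: 0.00605 × 39 = +23.6%.
- With a ratio of 10 instead: 0.001 × 9 = +0.9% and 0.00605 × 9 = +5.4%.

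HIV diagnoses, even with zero risk on PrEP: the rate falls by the share f, which is 0.2% at 3 million, 0.6% at 1 million and 1.2% at 0.5 million.

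The HIV-testing and STI-diagnosis figures arise only through current or resuming users, since Table 2 alone governs those endpoints. STI testing is also exposed to the conflict between the lists, but the protocol gives no STI testing rate from which to size it.

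**The case against.** The strongest reply is that the protocol restricts this cohort to people off PrEP wherever it names it, including the 7.2.1 heading and the Table 2 row title. On that reading the PrEP-history item means past use, and the gap or look-back rule can be left to a statistical analysis plan, which was not available here. Much of this stands. A reader might infer that current users will be enrolled; the documents do not support that. They can enter only if the itemised list is applied without its heading. The reply is not complete, though. In the same section the oral cohort is headed as oral only, and its exclusion of CAB LA recipients is still spelled out. Nothing says which of the protocol's PrEP gap rules, if any, would define being off PrEP. The conflict between two printed censoring lists is in the protocol itself and is not a detail left for later.

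The other replies also have weight. The lists conflict for two endpoints, not four. The 6,050 were prescribed PrEP at some time in 2022 and were not all on it for 12 months. The 40-fold STI ratio is assumed and covers two of eleven listed infections. The study is descriptive, and Section 7.9 already concedes a broad cohort, although that concession concerns missing behavioural detail and not PrEP status.

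A reader might also infer that the HIV diagnosis rate is materially understated, or that rates among men who have sex with men or people with a PrEP history are badly distorted. The arithmetic does not support the first. On the second, no such subgroup rates are planned for Objective 2.2.

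**Conclusion.** The point holds as a contradiction between Table 2 and Section 7.3.3, together with a cohort restriction that is stated but not put into effect. Following 7.3.3 as written puts follow-up after PrEP start into rates for people off PrEP. Following Table 2 as written keeps follow-up after HIV diagnosis in the denominator.

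The likely result is a modest upward bias in testing and STI rates and a negligible effect on the overall HIV diagnosis rate. The exact size cannot be fixed from the protocol, because it gives neither the cohort size nor the off-PrEP rates; the upper figures need a small cohort, a low off-PrEP rate and full-year PrEP use by everyone counted. This should be fixed before the analysis data set is built, but it does not threaten the study.

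**What to change.** 1. Use one censoring list in Table 2 and Section 7.3.3 for all four Objective 2.2 endpoints: the first of HIV diagnosis, PrEP initiation or resumption, 12 months after index, death, loss to follow-up and end of the study period.
2. Add to 7.2.1 and Table 2 an item requiring the Veteran to be off PrEP at the index date. Define it consistently with the discontinuation rules already used for Objective 3: no refill within 30 or 90 days for oral PrEP (state which applies) and more than 127 days without injection for CAB LA. A definition based on the 37- and 67-day coverage windows would call someone off PrEP whom Objective 3 still treats as in continuous use. The protocol has no corresponding rule for lenacapavir, so one must be stated for this analysis.
3. Limit the PrEP-history item to past use.
4. Say whether someone on PrEP at the first qualifying visit is excluded or indexed at a later off-PrEP visit.

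The cost is wording in three places. The PrEP dispensing and injection records are already needed for Objective set 3, so no new data are required.

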have not consistently used a condom, or have been diagnosed with a sexually transmitted infection (STI) in the past six months (US CDC, 2024). PrEP is also recommended to people who inject drugs and have an injection partner with HIV, or share needles, syringes, or other equipment to inject drugs. People who have been prescribed PEP (post-exposure prophylaxis) and report continued risk behavior or have used multiple courses of PEP may as well consider taking PrEP. People may also choose to take PrEP, even if these behaviors do not apply to them.

In 2022, of approximately 1.2 million people in the US who could benefit from PrEP, it was estimated that only around 36% had received a PrEP prescription (Fanfair, 2023). The Department of Veterans Affairs (VA) is the largest HIV care provider in the US; PrEP is a covered benefit for all enrolled Veterans (Huang, 2018). An analysis of 2014-2022 data of the Veterans Health Administration (VHA) showed an increase in the number of Veterans prescribed PrEP annually, from 361 in 2014 (5.6 per 100,000 Veterans in VHA care) to 6050 in 2022 (89.4 per 100,000) (Huang, 2025). While adherence to oral PrEP was high among Veterans in the period 2012-2016 (Huang, 2018), recent adherence data, including for long-acting injectable PrEP, are lacking. To be eligible for CAB-LA PrEP in the Veterans Health Administration, individuals must be at substantial risk of HIV acquisition (sex without condoms, recent or frequent sexually transmitted infections, sexual relationship with HIV infected partner, injection drug abuse with equipment sharing), prescribed cabotegravir by a provider experienced in PrEP, and meet at least one of the following additional criteria: intolerance to TDF/FTC or TAF/FTC, renal dysfunction, challenges with adherence to daily oral PrEP, or very high risk of HIV acquisition. Patients are excluded if they have significant noncompliance with follow-up or drug interactions with CAB (VA, 2022).

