**Objective set 2- Veterans in care with no evidence of HIV infection who are not on PrEP but could benefit from PrEP**

- 2.1- Describe the characteristics of Veterans in care who are not on PrEP but could benefit from PrEP
- 2.2- Estimate HIV testing and diagnoses rates, as well as rates of STI screening/testing rates, STI diagnoses among Veterans in care who are not on PrEP but could benefit from PrEP, over a 12-month period of follow-up

**Objective set 3- Veterans on care with no evidence of HIV infection who initiate PrEP (oral or CAB LA injectable) during the study period**

- 3.1- Describe the population of Veterans in care who initiated oral PrEP or CAB LA injectable PrEP, including their demographic, clinical and sexual behavioral characteristics, the year of PrEP initiation and the duration of follow-up
- 3.2- Describe the proportions of Veterans on care initiating CAB LA PrEP who used oral lead in (OLI) and proportion of those with direct to injection (DTI).
- 3.3- Describe adherence to oral and CAB LA injectable PrEP
- a) Oral PrEP use only: number days oral PrEP supplied divided by number of days in observational period
  - b) CAB LA injectable PrEP
    - Number of days covered by CAB LA PrEP divided by the number of days in the observation period
    - Timing and completion of initiation injections
    - Among complete initiators with at least one maintenance injection, timing of maintenance injections: all on time, any late injection (short delay not requiring reinitiation, long delay requiring reinitiation)
    - Baseline characteristics of users with all injections on time versus users with any late maintenance injection
- 3.4- Describe patterns of PrEP use
- a) Oral PrEP:
    - Discontinuation: any discontinuation, resumption of oral PrEP
    - Duration of oral PrEP use for the first period of use
  - b) CAB LA injectable PrEP
    - Discontinuation: any discontinuation, resumption of long-acting injections (with CAB LA injectable or LEN LA injectable) or oral PrEP after discontinuation
    - Oral bridging between discontinuation of CAB LA injections and resumption of CAB LA injections
    - Duration of CAB LA PrEP use in months

- first period of use
  - cumulative use throughout the study period in case of discontinuation followed by resumption of CAB LA PrEP injection(s)
  - Baseline characteristics of users discontinuing CAB LA PrEP versus users who did not discontinue

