  - Proportion of CAB LA PrEP users with at least one maintenance injection who are on CAB LA PrEP at 12 months and 24 months after initiation and at the end of the study period
- 3.5- Described patterns of HIV and other STI testing/screening, diagnosis and STI treatment
- a) Assess the incidence of HIV testing and HIV diagnosis during the first period of PrEP use by PrEP modality
  - b) Estimate the frequency of testing for STI diagnosis and STI diagnosis by PrEP modality
    - in the 6 months preceding PrEP initiation
    - during the first period of PrEP use
  - c) Describe the proportion of diagnosed STI with a relevant antimicrobial prescription
- 3.6- Among CAB LA PrEP users diagnosed with HIV (during CAB LA PrEP use or after CAB LA PrEP discontinuation)
- a) Describe the timing of incident HIV diagnoses relative to timing of CAB LA PrEP usage and testing for HIV
  - b) Describe adherence to PrEP injection schedule, HIV treatment, virologic suppression, concomitant STI diagnosis, and HIV drug resistance

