##### **Veterans using PrEP (Objective set 3)**

**Objective 3.1-** Baseline demographic and clinical characteristics will be described at the start of PrEP use during the study period, by regimen type (oral or CAB LA), using median and interquartile ranges for continuous variables and counts and proportions for categorical variables.

**Objective 3.2-** The proportions of Veterans on care initiating CAB LA PrEP who used oral lead in (OLI) and proportion of those with direct to injection (DTI) will be calculated.

**Objective 3.3 and 3.4-** PrEP adherence and usage patterns will be described using median and interquartile range for continuous data as well as absolute and relative frequencies for categorical data. The percentage of days with access to oral PrEP and CAB LA PrEP will be described over the first 12 months after index PrEP initiation. Characteristics of individuals with and without delayed CAB LA injections as well as individuals with and without discontinuation will be compared using Pearson's chi-square tests for categorical variables and Mann-Whitney tests for continuous variables.

**Objective 3.5-** Incidence rates and confidence intervals for HIV testing, HIV diagnosis, STI testing/screening and STI diagnosis will be calculated using univariate Poisson regression. STI treatment prescription will be described using absolute and relative frequencies for categorical data.

**Objective 3.6-** For CAB LA PrEP users diagnosed with HIV, a timeline including details of oral PrEP prescriptions prior to CAB LA PrEP start, injections received, HIV tests performed, HIV treatment, viral load measurements, HIV drug resistance will be provided for each individual.

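### Neither objective set 3 cohort requires a PrEP-free look-back, so the six-month window before PrEP initiation in Objective 3.5b mixes pre-PrEP time with time already on PrEP

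*Protocol*

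**What the plan says.** Section 6 defines objective set 3 as Veterans "who initiate PrEP (oral or CAB LA injectable) during the study period". The entry rules in Section 7.2.1 are wider:

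- **CAB LA cohort:** "Received at least one CAB LA PrEP injection between January 1, 2021 and June 30, 2025", with "No evidence of HIV infection at the time of the first CAB LA PrEP injection in the study period". No condition is placed on earlier or current oral PrEP.
- **Oral cohort:** at least one oral prescription in the entry window and HIV-free status at the first in-period prescription. It also requires "Have not received a CAB LA PrEP injection between January 1, 2021, and June 30, 2025", so a Veteran who moved from oral PrEP to CAB LA by that date is analysed only as a CAB LA user. No PrEP-free period is required here either.

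Table 2 (Section 7.1) gives the index date as "Start of first PrEP regimen during the study period (dispensing date for oral PrEP, injection date for CAB LA". Section 7.7.1.1 says that baseline characteristics for Objective 3.1 "will be described at the start of PrEP use during the study period", by regimen type.

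Objective 3.5b (Section 6) asks for STI testing and diagnosis by modality in two periods: "in the 6 months preceding PrEP initiation" and the first period of use. Section 7.3.3 specifies the during-use period for STI testing and adds nothing about the preceding window.

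**The concern.** The label on the first 3.5b period says that PrEP had not yet begun. That is true only if index is the start of PrEP for the Veteran, and the entry rules do not ensure it in either cohort.

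The protocol itself leads one to expect the exceptions. Section 5 lists the additional VHA criteria for CAB LA, of which at least one must be met: "intolerance to TDF/FTC or TAF/FTC, renal dysfunction, challenges with adherence to daily oral PrEP, or very high risk of HIV acquisition". The first and third of these imply experience with oral PrEP in at least some users. The Objective 3.6 timelines are to list oral prescriptions before CAB LA. For the oral cohort, Section 5 reports VHA PrEP prescribing from 2014 onwards, so some Veterans will already have been on oral PrEP on January 1, 2021.

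At stake are the preceding-window STI testing and diagnosis rates in each modality. Section 5 says that people on oral PrEP are seen every three months and that STI screening is part of PrEP follow-up. On-PrEP time is therefore monitored differently from time before any PrEP. A reader who sets the two 3.5b periods next to each other, or the two modalities, would be looking at unknown mixtures.

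**Working it through.** **1. The plan's own figure.** Section 7.5 gives 77-83% for a proportion of 80% with N = 748. Check: 1.96 × √(0.8 × 0.2 / 748) = 0.0287, so 0.771 to 0.829. It reproduces, and it does not depend on the index date.

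**2. Which index date the text supports.** Table 2 opens with the first PrEP regimen but names the injection date for CAB LA. HIV-free status (7.2.1), the coverage rule, total follow-up and months on regimen (7.3.3) all run from the first CAB LA injection. The 12- and 24-month windows are CAB LA rules that make sense only from there. First injection is the better-supported reading, and it is used below.

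**3. On-PrEP share of the preceding window, one Veteran.** Let g be the days from the start of continuous oral PrEP to the first injection, and take six months as 182 days. Share w = min(g, 182) / 182.

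| g (days) | w |
|---|---|
| 30 | 30/182 = 16% |
| 90 | 90/182 = 49% |
| 180 | 180/182 = 99% |
| 270 or more | 100% |

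A Veteran whose oral supply ended more than six months before the injection has w = 0. In the oral cohort, an ongoing user with continuous supply through the six months before the first in-period dispensing has w = 100%.

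**4. On-PrEP share of the CAB LA group's window.** The protocol does not give the share f of direct switchers among the 748. Assume a range, a common gap g, and a full 182-day window for everyone. The on-PrEP fraction of person-time is s = f × w.

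| f (assumed) | Veterans | s at g = 90 | s at g = 180 |
|---|---|---|---|
| 10% | 75 | 5% | 10% |
| 25% | 187 | 12% | 25% |
| 50% | 374 | 25% | 49% |
| 75% | 561 | 37% | 74% |
| 90% | 673 | 45% | 89% |

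**5. Effect on the reported rate.** If r0 is the rate in time before PrEP and r1 the rate on oral PrEP, the pooled rate is (1 − s) r0 + s r1. It differs from r0 by s (r1 − r0). The documents give neither rate, so the size cannot be stated further. With regular on-PrEP screening the testing rate would be pulled upwards. The direction for diagnoses is not fixed by the text.

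**6. What the other index reading would do.** If index were the first oral dispensing, 12-month CAB LA coverage for a Veteran with every injection on time would be (365 − g)/365: 335/365 = 91.8% at g = 30, 75.3% at 90, 50.7% at 180, 26.0% at 270 and 0% at 365 or more. From the first injection it is 100% throughout. This shows why the wording should be tightened. It is not the expected result of the plan.

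**The case against.** The best defence has four parts.

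- **The index is settled.** A reader might infer from the phrase about the first regimen in Table 2, and the start of PrEP use in 7.7.1.1, that the index is contradictory and that CAB LA adherence and persistence will be understated for switchers. The documents do not support that. The Table 2 parenthesis and the CAB LA rules in 7.2.1 and 7.3.3 point to the injection, and the 7.7.1.1 sentence goes on to say by regimen type. Even under the oral-date reading, persistence at the fixed time points could move either way, because a switcher would be judged after fewer months of injections. This part of the defence stands, and only loose wording remains.
- **The oral group is no cleaner.** A reader might take the oral cohort as moving from no PrEP to PrEP, with only the CAB LA cohort mixed. That is not so, because the oral cohort has no washout either. This widens the point: a correction to CAB LA alone would leave the display mixed.
- **The study is descriptive.** No before-and-after contrast or test between modalities is planned for 3.5b. That is true and limits the harm. But a descriptive rate still has to describe what its label says.
- **Prior use is recorded.** Section 7.3.2 lists history of PrEP use at baseline, and an SAP could add subgroups. The variable will show that prior users exist. It does not set the index, the window or any split, and the window's label is fixed in the protocol.

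A reader might also infer that oral failure is the main route to CAB LA, or that every switcher's window is wholly on PrEP. Section 5 lists alternative criteria, and two of them, renal dysfunction and very high risk, need no earlier oral use. The window is on PrEP only as far as supply falls within it.

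**Conclusion.** The point holds for the 3.5b preceding window, in both cohorts. Under the index the protocol best supports, that window pools pre-PrEP and on-PrEP time for an unknown part of each group. For one Veteran the on-PrEP share runs from 0% to 100%, depending on when oral supply began and ended. For the CAB LA group it runs from 5% to 89% over the assumed shares and gaps shown. These figures rest on continuous oral supply up to the injection, a common gap and a complete window. The share of switchers among the 748 and of ongoing users among the 15,477 is not in the document.

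The index wording for switchers needs tightening but is not a working contradiction. Coverage, persistence and Table 4 are unaffected if the first injection is used. The change is worth making before analysis because it alters reported rates at little cost.

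**What to change.** 1. In Table 2 and Section 7.7.1.1, state that the CAB LA index is the first CAB LA injection in the entry window, whatever oral PrEP came before.
2. In both cohorts, flag any PrEP supply in the six months before index from the dispensing and injection records. Say whether cabotegravir tablets given as oral lead-in count, since otherwise every lead-in user would be flagged.
3. Report 3.5b by this flag, and describe 3.1 by it. Present the preceding window as a pre-PrEP rate only for Veterans without recent PrEP, and label it *on prior PrEP* for the others.

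**Cost.** Protocol wording and one derived variable. For index dates early in 2021 the look-back reaches into 2020. Section 7.4 describes the sample as covering patients with VA care since 2000, and the baseline variables already need earlier data. The price is precision. If the 748 split evenly, a proportion of 80% in 374 Veterans has a 95% interval of width 2 × 1.96 × √(0.8 × 0.2 / 374) = 0.081, against 0.057 for all 748.
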